#### **4.5 Participant Retention**

Once a participant is enrolled, study staff will make every effort to retain the participant for the protocol-specified duration of follow-up thereby minimizing potential biases associated with loss to follow-up. Only participants who demonstrate understanding through the comprehension assessment conducted during the informed consent process, including what will be expected of them during study participation, will be enrolled in the study.

To minimize loss-to-follow-up, all participants who require follow-up visits will be provided with an appointment card with a date of their next visit and the contact numbers of our study staff. We will continuously counsel participants about the importance of adhering to their scheduled visits in the study. To facilitate adherence, we will also provide transport reimbursement (in accordance with NHSRC requirements) and refreshments in the waiting area at the study clinic. During their waiting time at the research clinic, we will also provide some educational materials and entertainment through the television that is in the

corridors of our research clinics. Over the years, we have noted that this minimizes boredom among participants while waiting for their study visit and results.

We plan to contact participants by phone or physical tracing a few days before their scheduled follow-up visits to remind them of their visits. We will use a standardized locator form to record essential participant tracing information (with participant permission), including phone numbers for the participant and family members/friends, landmarks close to the participant's home (churches, schools, shops, etc.), drawn maps of the participant's home and village, the name of the village chief and other contacts, and GPS coordinates (if a participant is traced and found to be at home). For missed scheduled follow up visit, a study community nurse or educator will make every effort to bring back the participant for the follow up visit except where participant withdraws consent or where it is not feasible due to unplanned relocation. The study community nurse or educator will contact participant within 1-3 days of missing their visit, through phone or physical tracing to find out the reason for missing the visits and offer re-scheduling of the visits. We will keep track of our retention rates on a weekly basis and discuss any retention issues experienced during the conduct of the study during the study team's weekly meeting.

#### **4.6 Removal of Patients from Protocol**

Regardless of the participant retention procedures referenced above, if a participant indicates that she no longer wishes to participate in the study, she will be allowed to withdraw from the study without losing any of her access to standard care. Participants may also be withdrawn from the study by the investigator or designee under the following circumstances:

- Participant re-locates away from the study site or is otherwise determined to be lost-to-follow-up after exhausting tracing efforts
- Investigator or designee determines that continued participation in the study would be unsafe or otherwise not in the best interest of the participant
- The study is stopped or canceled by the sponsors, government or regulatory authorities, or site IRBs/ECs

For any participant who is withdrawn from the study prior to scheduled completion of follow-up, study staff will document the reason for the withdrawal in detail and will make every effort to complete final evaluations as is allowable by the participant at the time. In the event that the circumstances that led to a participant's withdrawal change while the study is still underway (e.g., she returns to the study site area after having re-located previously), the site investigator or designee might consider options for resumption of follow-up.

## 5.0 TIME AND EVENTS TABLE

### 5.1 Schedule of study procedures

Study Visit	Screening & Enrollment	Week 4	Week 24	Week 28
Women who will attend the study visit	All women	Women who had cervical biopsy or cervical pap smear, and ECC done at Screening & Enrollment	Women who had CIN1+ at Screening & Enrollment and underwent thermocoagulation	Women who attended the Week 24 Visit
Evaluations				
Informed consent	X			
Baseline survey	X			
Urine pregnancy testing	X	X	X	
HIV-1 Rapid Test (2 kits)	X			
HIV-1 Confirmatory Test 	X			
CD4+ T cell count 	X			
HIV-1 RNA (plasma) 	X			
Self-collected vaginal brush	X			
hr-HPV testing of self-collected samples	X		X	
hr-HPV and S5 methylation testing of urine sample	X			
Provider-collected cervical brush	X 		X	
hr-HPV testing of provider-collected cervical sample	X 			
S5 methylation testing of provider-collected cervical sample	X 			
VIA 	X			
Colposcopy and cervical biopsy or cervical pap smear, and ECC 	X		X	
Thermocoagulation 	X			
Thermocoagulation-related adverse events evaluation		X		
Provide results and any referrals		X		X
Follow-up questionnaire 		X		
Enroll for IDIs	X	X		

For those with discordant HIV rapid tests.

For HIV-positive participants only

For all hr-HPV+ and for every 10th woman who is hr-HPV-.

Cervical biopsy and ECC if lesion seen at colposcopy; Cervical pap smear and ECC if no lesion seen at colposcopy

For women with ablation-eligible cervical lesion at colposcopy.

For follow-up of cervical histology and/or cytology results from Screening/Enrollment and to assess for any change in history or adverse events from thermocoagulation (if thermocoagulation was performed).

## 6.0 STATISTICAL CONSIDERATIONS

### 6.1 Study Design

This is a single arm, prospective study of 1,250 women (625 HIV-positive and 625 HIV-negative) recruited from outpatient clinics in Lilongwe, Malawi. The primary objectives of this study are to assess completion of a novel ICC screen-and-treat strategy among women, including HIV-positive women, in Lilongwe, Malawi, using self-collected vaginal brush for hr-HPV testing, followed by same-day VIA and thermocoagulation for HPV-positive/VIA-positive/ablation-eligible (by colposcopy) women, and to determine the 24-week efficacy of thermocoagulation among women with CIN2/3. The secondary objectives will be to evaluate the performance of the ICC screen-and-treat strategy by estimating overtreatment for women who are HPV-positive/VIA-positive/ablation-eligible, and undertreatment among HPV-positive/VIA-negative women, and to explore women's experiences with the proposed screen-and-treat algorithm.

### 6.2 Sample Size and Accrual

We anticipate enrolling 625 women over approximately 260 days. This enrollment target assumes a screening to enrollment ratio of 10 to 9, with 2-3 women enrolled/day, which is very feasible and allows adequate time for informed consenting, same-day screening with hr-HPV testing, triage with VIA, and thermocoagulation for VIA positive, ablation-eligible (by colposcopy) women, and also sufficient time for scheduled follow-up visits for already-enrolled women. Based on prior studies done among HIV-positive women in SSA, we assume that at least 50% (n=313) of the 625 HIV-positive women will be positive for hr-HPV and that at least 20% of these 313 women will have CIN2/3, which gives us at least 63 HIV-positive women with CIN2/3 in our cohort. Among HIV-negative women, we assume that at least 20% (n=125) of the 625 HIV-negative women will be positive for hr-HPV and that at least 10% of these women will have CIN2/3, which gives us at least 13 HIV-negative women with CIN2/3 in our cohort.

We assume that 5% of the 76 women with CIN 2/3 will be lost-to-follow-up after 24 weeks (95% is the typical rate of retention for studies done at UNC Project-Malawi at 6-month follow-up). Therefore, we will be able to determine the 24-week efficacy of thermocoagulation among approximately 72 women, including 60 HIV-positive women, with CIN2/3. This sample size of 72 CIN2/3 women, 60 of whom are HIV-positive, is comparable with other studies included in a meta-analysis that evaluated the efficacy of thermocoagulation for treating CIN2/3. Assuming treatment efficacy of 90% over 24-weeks follow-up, we should have >95% confidence to measure the efficacy within  $\pm$  8% for the overall sample and the HIV-positive sub-group.

For the IDIs, up to 30 women will be recruited at Screening/Enrolment Visit or Week 4 Visit. The IDIs will explore participants' experiences with the proposed ICC screen-and-treat strategy among women. We expect to reach thematic saturation with this sample size, based on prior work showing that few new themes are established after the first 18 interviews. We expect significant overlap in themes between the HPV-positive and HPV-negative groups.

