For all women who undergo VIA, we will determine if a woman is VIA-positive and ablation-eligible using colposcopy with Mobile ODT EVA system. Women who are VIA-positive will undergo colposcopically-directed biopsies of the acetowhite lesion, with at least 2 and up to 4 biopsies taken, as well as an ECC. If the woman is still considered to be ablation-eligible by colposcopy, she will then undergo thermocoagulation. Women who are VIA-negative will also undergo colposcopy, and at least 2 and up to 4 cervical biopsies and ECC if a lesion is seen at colposcopy. Thermocoagulation will also be performed on these women if they are found to have an ablation-eligible lesion on colposcopy. If no lesion is seen on colposcopy, the woman will have cervical pap smear and ECC collected, and no thermocoagulation will be performed. Women who are suspicious for cancer at VIA will undergo colposcopically-directed cervical biopsies. Whenever biopsy is indicated, we will perform at least 2 cervical biopsies on women because previous studies have shown that cervical biopsy is most sensitive when at least 2 biopsies are taken. During colposcopy, images of the cervix may be captured with the EVA system. These images will be stored only in password-protected and de-identified study databases, linked only to the study participant PID. The images will be used for internal quality assurance and may also be shared with the sponsor or other parties for research purposes.

For women to undergo thermocoagulation, we will consider them to be ablation-eligible if the following criteria are met at colposcopy: 1) cervical lesions are not suspicious for ICC; 2) cervical lesions are located entirely on the ectocervix; 3) cervical lesions are no more than 2-3 mm into the endocervical canal; 4) the entire squamocolumnar junction (SCJ) can be visualized; and 5) all visible lesions are deemed appropriate for thermocoagulation by the treating provider. Women with suspected endocervical dysplasia, CIS, or ICC will be referred for treatment at the Kamuzu Central Hospital (KCH), a public tertiary and teaching hospital Colposcopy Clinic on which campus UNC Project-Malawi is situated.

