#### **Week 4**

All women who had cervical biopsies or cervical pap smear, and ECC done at Screening/Enrollment will return for histology and/or cytology results at Week 4. HPV-positive/VIA-negative women without CIN or ICC on histology and those with normal cytology will be advised to continue with routine ICC screening per guidelines. Women who underwent thermocoagulation will be evaluated for interval medical history or post-treatment adverse events during this visit. HPV-positive/VIA-negative women with CIN2+ on ECC or abnormal cytology on cervical pap smear will be referred to KCH Colposcopy Clinic for further management.

HPV-positive/VIA-positive women who had CIN detected at baseline cervical biopsy, and underwent thermocoagulation will be followed up at Week 24 post-treatment. Women who had CIN and visible cervical lesion that was not ablation-eligible by colposcopy or had ICC will be referred to KCH Colposcopy clinic for further management.

Women who are HPV-positive may be enrolled in and consented for IDIs at their Week 4 visit. These interviews will be conducted similarly to those done at the Screening/Enrollment visit but they will also cover women's experiences sharing their screening results with others and abstaining from sex for the recommended interval after biopsy/thermocoagulation.

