With an expected 76 CIN2/3 lesions among our participants and 90% hr-HPV positivity at time of treatment, we estimate that 68/76 women who undergo thermocoagulation at Screening/Enrollment will be hr-HPV positive. Accounting for 5% loss to follow up by week 24, we will have a sample of 65 women who were hr-HPV positive at time of treatment present for repeat hr-HPV testing. With these 65 women, we will have 99.9% power to detect a difference between hr-HPV positivity pre- and post-treatment, assuming 100% hr-HPV positivity pre- and 35% hr-HPV positivity at 24 weeks post-treatment. We assume that 35% will still be hr-HPV-positive based on a recent systematic review, finding that 35% of women were still hr-HPV-positive after cryotherapy; no such estimates are available for thermocoagulation. In addition, no estimates are currently-available for the 24-week for CIN1 as thermocoagulation has not been used to treat low-grade dysplasia. Hr-HPV results at the Week 24 visit for non-CIN-2/3 cases at enrollment will be investigated in exploratory analyses, stratified by baseline CIN1 and normal/cervicitis status.

**Secondary objective I:** To evaluate performance of ICC screen-and-treat strategy among women, including HIV-positive women, by estimating overtreatment for

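### The 72 evaluable CIN2/3 women (60 HIV-positive) in section 6.2 assume that every expected case is ablated; the treatment step is missing and the HIV-positive ±8% has little room for it

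*Combined protocol and SAP*

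**What the plan says.** Section 6.2 builds the efficacy sample in steps. Of 625 HIV-positive women, at least 50% (313) are expected to be hr-HPV positive and at least 20% of those to have CIN2/3, "which gives us at least 63 HIV-positive women with CIN2/3 in our cohort". The same steps for 625 HIV-negative women (20%, then 10%) give at least 13, for a total of 76. One deduction follows: "We assume that 5% of the 76 women with CIN 2/3 will be lost-to-follow-up after 24 weeks". The result is "Therefore, we will be able to determine the 24-week efficacy of thermocoagulation among approximately 72 women, including 60 HIV-positive women, with CIN2/3". On precision: "Assuming treatment efficacy of 90% over 24-weeks follow-up, we should have >95% confidence to measure the efficacy within" ±8%, for the whole sample and for the HIV-positive sub-group.

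Section 6.3, primary objective II, takes the same 76 as treated: "we estimate that 68/76 women who undergo thermocoagulation at Screening/Enrollment will be hr-HPV positive". From this it derives 65 women for the hr-HPV clearance analysis.

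The conduct sections make treatment conditional:

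- Section 4.3, Screening & Enrollment, lists five colposcopic criteria and says: "If the woman is still considered to be ablation-eligible by colposcopy, she will then undergo thermocoagulation". If no lesion is seen, there is no thermocoagulation.
- Section 5.1, footnote 5, limits thermocoagulation: "For women with ablation-eligible cervical lesion at colposcopy".
- Section 4.3, Week 4: "Women who had CIN and visible cervical lesion that was not ablation-eligible by colposcopy or had ICC will be referred".
- Section 4.3, Week 24, and section 5.1 bring back treated women with CIN1 or worse for the efficacy assessment. Women who were referred are followed up then to confirm that they received care.
- Section 6.3, primary objective I, plans to count women who are not eligible for thermocoagulation but are suitable for LEEP.

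On accrual, section 6.2 describes 625 women over about 260 days at 2-3 per day. Section 4.1 plans 1,250 women over 12 months.

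**The concern.** The estimand of primary objective II is cure after thermocoagulation, so a woman who is not ablated cannot contribute to it. The sample size chain goes from women who have CIN2/3 to women evaluable after treatment without passing through treatment. The design expects some women with CIN2/3 to leave at that step: those with an ineligible lesion, those with no visible lesion whose disease is found only on ECC, and any who are not treated for other reasons.

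The ±8% is the only precision stated for this objective. It is claimed expressly for HIV-positive women, the group in which section 7.4 says data on the device are limited. If the treated share is below 100%, the stated counts and precision are better than the design would give at the stated yields.

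**Working it through.** **Inputs from section 6.2.** 63 HIV-positive and 13 HIV-negative CIN2/3 cases; 5% loss; efficacy p = 0.90; half-width 8 points at 95% confidence. No interval method is named.

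**The plan's figures reproduce.**

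- Counts: 76 × 0.95 = 72.2 and 63 × 0.95 = 59.85, stated as 72 and 60.
- Wald half-width, 1.96 × √(0.9 × 0.1 / n): n = 72 gives 6.9 points and n = 60 gives 7.6 points. Both are within 8.

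**Number needed for ±8% (Wald).** 1.96² × 0.09 / 0.08² = 54.02. In whole women this is 55, because 54 gives 8.002 points and 55 gives 7.93.

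**Adding the missing step.** Let f be the share of expected CIN2/3 cases that are ablated. Evaluable women are 63 × f × 0.95 (HIV-positive) and 76 × f × 0.95 (overall).

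- HIV-positive threshold: 54.02 / 59.85 = 90.3% unrounded; 55 / 59.85 = 91.9% in whole women. Hence about 90-92%.
- Overall threshold: 54.02 / 72.2 = 74.8%; 55 / 72.2 = 76.2%. Hence about 75-76%.

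The documents give no value for f. The range below is an assumption. The last column is 76 × f × 0.90 × 0.95, against the 65 stated in section 6.3.

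| f (assumed) | HIV-positive n | Wald ± | Overall n | Wald ± | hr-HPV clearance n |
|---|---|---|---|---|---|
| 100% | 59.9 | 7.6 | 72.2 | 6.9 | 65 |
| 95% | 56.9 | 7.8 | 68.6 | 7.1 | 62 |
| 90% | 53.9 | 8.0 | 65.0 | 7.3 | 58 |
| 80% | 47.9 | 8.5 | 57.8 | 7.7 | 52 |
| 70% | 41.9 | 9.1 | 50.5 | 8.3 | 45 |

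**Dependence on the interval method.** The Wilson half-width is 7.7 points at n = 60, 7.95 at n = 57 and 8.02 at n = 56, so its HIV-positive threshold is 57 / 59.85 = about 95%. The Clopper-Pearson interval for 54 of 60 is 79.5% to 96.2%. Its lower arm is 90.0 − 79.5 = 10.5 points, so it exceeds 8 with everyone ablated.

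**Possible offsets.**

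- At f = 80%, 55 evaluable HIV-positive women are kept if the CIN2/3 rate among hr-HPV positive women is 55 / (312.5 × 0.95 × 0.80) = 23.2%, not the stated minimum of 20%.
- Every 10th HPV-negative woman also has colposcopy and can be ablated. Among HIV-positive women that is (625 − 313) / 10 = about 31. At an assumed 5% CIN2/3, all ablated, they add 31.2 × 0.05 × 0.95 = about 1.5 evaluable women.

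**Accrual.** 625 / 260 = 2.4 per day, which matches the stated 2-3. 1,250 / 260 = 4.8 per day, which does not.

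**The case against.** The strongest reply is that every yield in section 6.2 is stated as a minimum and that 72 is stated as approximate. A modestly higher CIN2/3 rate would replace the women lost at the treatment step, and the HPV-negative sample may add one or two. This stands. A reader might infer that 72/60 is a ceiling, or that the trial will miss its precision. The documents support neither reading: the margin in the yields depends on sources that are not before us, and the ablated share is not stated.

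A second reply is that the threshold is not sharp. This also stands. The 92% arises from rounding 54.02 up to 55 women. With 57 of 63 treated, the unrounded n is 54.15 and the half-width 7.99 points. If ±8% is read as a figure rounded to a whole percent (below 8.5), it survives to about 80% ablated. On the other side, Wald is the method most favourable to the plan among those tried.

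A third reply is that the effect is small. Going from 100% to 80% ablated costs the HIV-positive group about 0.9 points. Section 6.3 plans only a comparison with a historic range of 85-95%, and no rule turns on ±8%. The 99.9% power for hr-HPV clearance is not in question here, only its count of 65.

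Two further inferences should not be drawn. Section 1.2 cites 39% hr-HPV prevalence in HIV-positive women and section 6.2 assumes at least 50%. The two figures have different citations, and choosing one of them is not an error. The Week 4 text mentions Week 24 follow-up for treated HPV-positive/VIA-positive women, but does not say that only they return, so it need not conflict with the broader statements elsewhere.

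None of this supplies the missing step. A possible surplus in one factor does not replace an unstated value of 100% in another.

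**Conclusion.** The point holds as an omitted step in a stated figure. Sections 6.2 and 6.3 count all 76 expected CIN2/3 cases as ablated, while the protocol treats only eligible lesions and refers the rest.

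At the stated yields, 95% retention and 90% efficacy, the HIV-positive ±8% needs about 54-55 of the 60 women. That is about 90-92% ablated by Wald and about 95% by Wilson; by Clopper-Pearson the lower arm is over 8 points from the start. The overall claim is fairly robust, holding to about 75-76% ablated (Wald).

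It is not shown that the study will fall short, and no test or decision rule is affected. The correction is worth making because this is the only precision given for a primary objective and the sub-group of most interest has the least slack. The accrual mismatch is separate and minor.

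**What to change.** In section 6.2, insert an explicit factor between expected CIN2/3 cases and evaluable women: the share expected to be ablation-eligible and treated, stated as an assumption with its basis and a range. Carry the same factor into the 76, 68 and 65 in section 6.3. Restate the evaluable counts and the half-widths over that range, chiefly for the HIV-positive sub-group, and name the interval method behind ±8%. If the authors rely on yields above the stated minimums to absorb the loss, one sentence should say so and give the rate needed.

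Separately, rewrite the accrual sentence for 1,250 women in 12 months, with a daily rate that matches.

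The cost is rewording section 6.2 and one paragraph of section 6.3. The stated HIV-positive precision may become slightly less favourable. No patients, visits or procedures are added, and no clinical rule changes.

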### 6.3 Data Analysis Plans

**Primary objective I:** To assess completion of a novel ICC screen-and-treat strategy among women in Lilongwe, Malawi, using self-collected vaginal brush for hr-HPV testing, followed by same-day VIA and cervical thermocoagulation for HPV-positive/VIA-positive/ablation-eligible (by colposcopy) women.

**Data analysis for primary objective I:** We will calculate the following proportions with corresponding 95% Confidence Intervals (CIs) for these two primary outcomes: a) the proportion of women who are HPV positive who have VIA performed same-day, and b) the proportion of women who are VIA-positive/ablation-eligible (by colposcopy) who have thermocoagulation performed the same-day. We hypothesize that >90% of women who are HPV-positive will have VIA performed same-day and that >90% of women who are VIA-positive/ablation-eligible (by colposcopy) will have thermocoagulation performed the same day.

We will also systematically monitor and analyze indicators for the completion of this novel ICC screen-and-treat strategy, as follows:

Number (and %) of women who received self-collection kit and who returned a self-sample
Number (and %) of HPV positive, negative, insufficient, and missing results from self-collection
Number (and %) of women who receive their HPV results the same day as collection
Number (and %) of HPV-positive women invited for VIA
Completion point 1:
Number (and %) of women with HPV-positive results who receive VIA same-day

Number (and %) of HPV-positive women who receive VIA on another day (instead of same-day)
Number (and %) of HPV-positive women who never receive VIA (loss to follow-up)
Number (and %) of HPV-positive women with VIA positive results
Number (and %) of HPV-positive women with VIA-positive results who are eligible for thermocoagulation by colposcopy; not eligible for thermocoagulation but LEEP eligible; or referred for suspected cancer
Completion point 2:
Number (and %) of women with VIA positive results and are ablation-eligible by colposcopy who receive thermocoagulation same-day
Number (and %) of women with VIA positive results and are ablation-eligible who receive thermocoagulation on a following day
Number (and %) of HPV-positive women with cervical biopsy or cervical pap smear, and ECC performed, and N (%) with histology and/or cytology read
Number (and %) of CIN2+, CIN1, or normal at Screening/Enrollment
Number (and %) of treated women who return for Week 24 follow up visit.
Number (and %) of treated women who return for Week 24 follow up visit and are found to have resolved versus persistent hr-HPV
Number (and %) of treated women who return for Week 24 follow up visiting that are found to have resolved CIN1
Number (and %) of treated women who return for Week 24 follow up visit that are found to have resolved CIN2+
Number (and %) of treated women who return for Week 24 follow up visit that are found to have persistent CIN1+
Number (and %) of treated women who return for Week 24 follow up visit that are found to have persistent CIN2+
Number (and %) of treated women who return for Week 24 follow up visit that are found to have resolved CIN1
Number (and %) of women referred for further management who have received appropriate management by Week 24

We will also calculate the median time needed to complete the proposed HPV testing, VIA triage, and treatment cascade by recording the times for each of the following steps.

- 1) Time that the participant received the self-HPV collection brush
- 2) Time that the participant returned the self-HPV collection brush
- 3) Time that the HPV test was initiated in the Xpert machine
- 4) Time that the HPV test was completed in the Xpert machine
- 5) Time that the participant received her HPV result
- 6) Time that the participant had her VIA completed (if applicable)
- 7) Time that the participant had her colposcopy completed (if applicable)
- 8) Time that the participant had cervical biopsies or cervical cytology, and ECC completed (if applicable)
- 9) Time that the participant had her thermocoagulation completed (if applicable)

Logistic regression models will be used to assess factors associated with completing the proposed testing and treatment cascade for both HPV-positive and HPV-negative women, such as HIV status, length of time on ART, travel time to

attend in-clinic appointments, knowledge of someone with any cancer, HIV-1 RNA load, and CD4+ T cell count. This objective is largely descriptive and, thus, formal power calculations are not made.

**Primary objective II:** To determine the 24-week efficacy of thermocoagulation among women, including HIV-positive women, with CIN2/3. Women who undergo thermocoagulation will have follow-up at 24-weeks post-treatment for colposcopy, provider collected cervicovaginal brush for hr-HPV testing, ECC, colposcopy-directed cervical biopsy and ECC (if lesion noted) or cervical cytology and ECC (if no lesion noted at colposcopy). We hypothesize that >90% with CIN2/3 on pre-treatment biopsy will have  $\leq$ CIN1 at their 24-week biopsy.

**Data analysis for primary objective II:** For efficacy of thermocoagulation, we will compare our 24-week cure rates for CIN 2/3 with thermocoagulation to historic cure rates for CIN 2/3 with cryotherapy (85-95%), the recommended ablative treatment modality for CIN 2/3 for resource limited countries. We will perform exploratory analysis to determine the following:

- a) 24-week efficacy for CIN1, by calculating the proportion of women who had CIN1 at Screening/Enrollment and then were found to have no cervical dysplasia at Weeks 24 after thermocoagulation treatment;
- b) hr-HPV clearance in HPV-positive women treated with thermocoagulation, by calculating the proportion with no hr-HPV at Weeks 24; and
- c) Risk factors for CIN2+ among HPV-positive women (i.e., age, age at first sexual intercourse, number of sexual partners, HIV status, length of time on ART, HIV-1 RNA load, CD4+ count) via multivariable logistic regression.

With an expected 76 CIN2/3 lesions among our participants and 90% hr-HPV positivity at time of treatment, we estimate that 68/76 women who undergo thermocoagulation at Screening/Enrollment will be hr-HPV positive. Accounting for 5% loss to follow up by week 24, we will have a sample of 65 women who were hr-HPV positive at time of treatment present for repeat hr-HPV testing. With these 65 women, we will have 99.9% power to detect a difference between hr-HPV positivity pre- and post-treatment, assuming 100% hr-HPV positivity pre- and 35% hr-HPV positivity at 24 weeks post-treatment. We assume that 35% will still be hr-HPV-positive based on a recent systematic review, finding that 35% of women were still hr-HPV-positive after cryotherapy; no such estimates are available for thermocoagulation. In addition, no estimates are currently-available for the 24-week for CIN1 as thermocoagulation has not been used to treat low-grade dysplasia. Hr-HPV results at the Week 24 visit for non-CIN-2/3 cases at enrollment will be investigated in exploratory analyses, stratified by baseline CIN1 and normal/cervicitis status.

**Secondary objective I:** To evaluate performance of ICC screen-and-treat strategy among women, including HIV-positive women, by estimating overtreatment for

women who are HPV positive/VIA positive/ablation-eligible, and undertreatment among HPV positive/VIA negative women. All HPV positive women and every 10th consecutive HPV-negative woman will undergo VIA. During VIA, we will determine if a woman is VIA-positive and ablation-eligible. Women who are VIA-positive will undergo colposcopically-directed cervical biopsies and endocervical currettings (ECC). If the woman is still considered to be ablation-eligible by colposcopy, she will then undergo thermocoagulation. Women who are VIA-negative will also undergo colposcopy, but they will only have cervical biopsies and ECC performed if a lesion is seen on colposcopy. Following VIA, we will collect directed cervical biopsies and ECC from VIA positive women prior to thermocoagulation treatment if ablation-eligible by colposcopy, or cervical pap smear and ECC from VIA negative women if no lesion is seen at colposcopy. If a lesion is seen at colposcopy, VIA negative will also undergo colposcopically-directed cervical biopsy and ECC. We hypothesize that <25% of HPV positive/VIA positive women would have been overtreated (no CIN2+, but treated) and that <30% of HPV positive/VIA negative women would have been undertreated (CIN2+, but untreated).

Data analysis for secondary objective I: Overtreatment will be calculated as the proportion of HPV positive/VIA positive/ablation-eligible women who would have been treated with thermocoagulation based on their HPV and VIA findings alone (without colposcopy), but were found to have no CIN2+ on colposcopically-directed cervical biopsy or ECC at Screening/Enrollment. This proportion will represent the women with no lesions or low-grade lesions (CIN1) who would have been unnecessarily treated if we based the decision to perform thermocoagulation on HPV and VIA testing alone.

Undertreatment will be calculated as the proportion of women with CIN2+ at Screening/Enrollment who were not treated or referred via our screening algorithm due to a negative HPV and/or VIA result. This proportion will represent the women with CIN-2+ who were missed by our HPV-and-VIA-based algorithm. For undertreatment, we will also evaluate the proportion of women who underwent thermocoagulation but were ECC positive for endocervical CIN2+, and therefore needed to be referred for further management since thermocoagulation does not adequately treat endocervical dysplasia. We have based our hypotheses on a recent review, which found that the pooled estimates for VIA sensitivity and specificity were 0.69 (95% CI 0.54-0.81) and 0.87 (95% CI 0.79-0.92), respectively, as well as from the high false positive rate for VIA found in our pilot study with nurses and clinicians in Malawi. These performance measures, however, were for primary screening, rather than as referral to treatment among HPV positive women.

In addition, to assess the potential for undertreatment of HPV-positive women, we will conduct VIA at Screening/Enrollment for every 10th women who is hr-HPV

negative. This sub-set analysis of HPV negative women undergoing VIA will allow us to control for potential verification bias. As all women will not be referred for verification by colposcopy, using only the histology results on HPV positive women to estimate disease burden could lead to biased inference. To correct for this verification bias, we will utilize the colposcopy results among the random sub-set of HPV-negative women to employ the maximum likelihood method proposed by Zhou. Estimates using this method are valid provided that the histology data are missing at random. This assumption means that for women with the same test results, those who were referred to colposcopy were similar to those that were not. Corrected CIN2+ burden will be estimated using maximum likelihood estimators (MLEs). This secondary objective is largely descriptive and, thus, formal power calculations are not made.

Secondary objective II: To explore women's experiences with the proposed ICC screen-and-treat strategy. Up to 30 women will undergo IDIs in their local language. They will first complete a questionnaire asking them to rate their privacy, embarrassment, discomfort, pain, and confidence during the screening/treatment process. Then, they will participate in in-depth interviews exploring their prior knowledge of cervical cancer, experience with the self-sampling, understanding of the results, and their intention to share screening experience with others. For women who are interviewed at Week 4, they will additionally be asked about their experience following the recommendation to abstain from sex for a specified interval.

Data analysis for secondary objective II: All IDIs will be recorded, and then the recorded interviews will be transcribed and translated into English. The translated interviews and any notes taken during the IDIs will then be analyzed for themes, subthemes, and codes. Modifications may be made to the interview guide throughout the qualitative study as new subthemes and ideas are uncovered which require further investigation.

Exploratory objective I:

(b) [REDACTED]

Exploratory objective II: [REDACTED]

